	eldo_controlled	2.0; Most Recent; Effective; CURRENT	090032d580db1b91	24-Oct-2017 08:49:05
	Reason For Issue	Auto Issue		

Sodium-calcium mixed partial salt of poly(methylvinylether/maleic acid) and carboxymethylcellulose

208397

Final Clinical Protocol, 20 Oct 2017

List of tables

Table 1-1	Schedule of Activities	10
Table 2-1	Study Objectives and Endpoints.....	15
Table 13-1	Abbreviation.....	57

GlaxoSmithKline Consumer Healthcare Confidential

Template Version Effective: 22-Jun-2017

Page 9 of 62

Document Name	208397 Clinical Protocol 2.docx	Document Identifier	Effective Date
Type	Version		
eldo_controlled	2.0; Most Recent; Effective; CURRENT	090032d580db1b91	24-Oct-2017 08:49:05

Sodium-calcium mixed partial salt of poly(methylvinylether/maleic acid) and carboxymethylcellulose

208397

Final Clinical Protocol, 20 Oct 2017

SCHEDULE OF ACTIVITIES

The schedule of activities table provides an overview of the protocol visits and procedures.

The investigator may schedule visits (unplanned visits) in addition to those listed on the schedule of activities, in order to conduct evaluations or assessments required to protect the well-being of the subject.

Table 1-1 Schedule of Activities

Procedure/Assessment	Screening	Study Period		
	Visit 1	Visit 2 Treatment Period 1	Visit 3 Treatment Period 2	Visit 4 Treatment Period 3
Informed consent	X			
Review Inclusion/Exclusion criteria	X	X	X	X
Demographics	X			
Medical history	X			
Current / Concomitant treatments	X	X	X	X
Dental history	X			
OST examination edentulous	X	X ^b	X ^b	X ^b
Clean dentures ^c	X	X	X	X
Criteria for well made and fitting dentures (retention, stability, clinical acceptability and denture finish)	X			
Food migration adequacy	X			
Subject eligibility	X			
Urine pregnancy test ^e		X	X ^d	X ^d
Randomisation		X		
Subject continuance		X	X	X
Treatment application and denture insertion ^a		X	X	X
Efficacy assessment - Food occlusion testing		X	X	X
Efficacy assessment - Number of denture dislodgements		X	X	X
Photograph of dentures (subset of subjects)		X	X	X
Subject-completed questionnaire		X	X	X
Adverse events		X	X	X
Incidents	X	X	X	X
Study conclusion				X

Abbreviations: OST = Oral Soft Tissue.

Any serious adverse event assessed as related to study participation that occurs subsequent to the signing of informed consent and any adverse event that occurs subsequent to the first dose will be recorded.

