3 STUDY DESIGN AND SUBJECT POPULATION

This will be a single centre, controlled, open label, randomised, three-treatment, three-period, cross-over design in subjects with full upper and full lower dentures. Each treatment period will consist of one day of testing with at least two days between adjacent treatment visits.

Approximately 48 (maximum 50) healthy subjects with both maxillary and mandibular full dentures will be enrolled in this study. In this study, subject recruitment will be targeted to achieve approximately equal numbers of subjects in the low and high Kapur-Olshan groups. The low Kapur-Olshan group is defined as a composite Kapur-Olshan score of 6-14 (clinically fair and good dentures) and the high Kapur-Olshan score as 15-18 (clinically very good dentures).

At the screening visit, following an OST examination, each subject's dentures (upper and lower) will be cleaned then assessed for retention and stability using the Kapur Index (Olshan Modification) ([Kapur, 1967](#); [Olshan, 1992](#)) and whether they are well made. Only those subjects with dentures (both upper and lower) that satisfy both of these criteria will undergo the food migration adequacy assessment to provide evidence of adequate peanut particle migration under the dentures after chewing a portion of peanuts. A visual observation and rating of location and extent of peanut particle migration adequacy must indicate > 0 on a 0 – 3 scale. Subjects meeting all the inclusion criteria with no exclusions will then be randomised at Visit 2. Subject recruitment will be controlled to ensure 50±10% of the subjects will be in each of the low and high Kapur-Olshan groups [the low Kapur-Olshan group is defined as a composite Kapur-Olshan score of 6-14 (clinically fair and good dentures) and the high Kapur-Olshan score as 15-18 (clinically very good dentures)]. There will be between 2-30 days between the screening visit and the for test day.

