4.2 Exclusion Criteria

Subjects who meet any of the following exclusion criteria will not be eligible for enrolment in the study:

1. An investigational site staff member directly involved in the conduct of the study or their family member, site staff members otherwise supervised by the investigator, or an employee of the sponsor directly involved in the conduct of the study.
2. Participation in any other clinical study involving investigational drugs, cosmetics or medical devices within 30 days prior to study entry and/or during study participation.
3. Acute or chronic medical or psychiatric condition or laboratory abnormality that may increase the risk associated with study participation or investigational product administration or may interfere with the interpretation of study results and, in the judgment of the investigator, would make the subject inappropriate for entry into this study.
4. Pregnant female subjects.
5. Breastfeeding female subjects.
6. Known or suspected intolerance or hypersensitivity to the study materials (or closely related compounds) or any of their stated ingredients.
7. Unwilling or unable to comply with the Lifestyle Guidelines described in this protocol.
8. History of swallowing difficulties or choking.
9. Currently taking or have taken a bisphosphonate drug (i.e., Fosamax®, Actonel®, Boniva®) for treatment of osteoporosis.
10. Any clinically significant or relevant oral abnormality (e.g. temporomandibular joint [TMJ] problems) that, in the opinion of the investigator, could affect the subject's participation in the study.
11. Known allergy to peanuts or any other nut.
12. Any condition or medication which, in the opinion of the investigator, is currently causing xerostomia.
13. Recent history (within the last year) of alcohol or other substance abuse.
14. OST examination findings such as stomatitis, open sores, lesions, redness or swelling which in the opinion of the investigator, would interfere with the conduct of the study.

[®] Fosamax is a registered trademark of Merck & Co.

[®] Actonel is a registered trademark of Warner Chilcott Company, LLC.

[®] Boniva is a registered trademark of Genentech.

 GlaxoSmithKline	Document Name	208397 Clinical Protocol 2.docx		
	Type	Version	Document Identifier	Effective Date
	eldo_controlled	2.0; Most Recent; Effective; CURRENT	090032d580db1b91	24-Oct-2017 08:49:05
	Reason For Issue	Auto Issue		

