5.7 Concomitant Treatments

Details of any relevant dental, medical or surgical history (within the last year), including allergies or drug sensitivity, will be recorded in the CRF. The use of concomitant medications is permitted in this study with the exception of the use of bisphosphonate drugs (exclusion criterion 9) and medications that in the opinion of the investigator would interfere with the conduct of this study (exclusion criterion 15).

Treatments taken after the first dose of study investigational product will be documented as concomitant treatments.

All concomitant treatments taken during the study must be recorded with indication, unit dose, daily dose, and start and stop dates of administration. All subjects will be questioned about concomitant treatment at each clinic visit.

Subjects will be asked not to have any non-emergency dental/denture work performed during the time they are in the study, unless discussed and permitted by the examiner. This is to assure that the denture fit will not be altered during the study.

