6 STUDY PROCEDURES

6.1 STUDY PERIOD

6.1.1 Screening - Visit 1

The following procedures/assessments will take place in the order listed below (where possible), and recorded in the CRF:

- Obtain written informed consent.
- Collect demography (year of birth, gender, race and ethnicity).
- Obtain medical history, including history of illegal drug, alcohol and tobacco use.
- Obtain [Dental History](#).
- Obtain complete medication history of all prescription or non-prescription drugs, and dietary and herbal supplements taken within 30 days prior to the planned first dose.
- Perform [OST Examination-Edentulous](#).
- Clean the subject's dentures using the supplied denture brush and cleansing paste, both the upper and lower dentures will be thoroughly cleaned to remove all traces of denture fixative, plaque and particulates/debris. Dentures should then be dried.
- Perform the [Well-Made Assessment](#).
- Perform the [Well-Fit Assessment](#).
- Perform the [Food Migration Adequacy Assessment](#).
- Review Inclusion and Exclusion criteria. Pregnancy status will be confirmed verbally by the subject.
- Assess subject eligibility.
- Any serious adverse event assessed as related to study participation that occurs subsequent to the signing of informed consent will be recorded.

To prepare for study participation, subjects will be instructed on the use of the [Lifestyle Guidelines](#) and [Concomitant Treatment\(s\)](#) sections of the protocol.

6.1.2 Visit 2

Subjects will be admitted to the clinical site between 2-30 days after Screening. The following procedures will be completed in the following order (wherever possible) and recorded in the CRF:

- Review Inclusion and Exclusion criteria. Pregnancy status will be confirmed verbally by the subject.
- Collect urine pregnancy test for females of childbearing potential.
- Confirm proper contraception is being used.
- Review changes in the subject's medical history including medication history since Screening.
- Perform [OST Examination-Edentulous](#).

 GlaxoSmithKline	Document Name	208397 Clinical Protocol 2.docx		
	Type	Version	Document Identifier	Effective Date
	eldo_controlled	2.0; Most Recent; Effective; CURRENT	090032d580db1b91	24-Oct-2017 08:49:05
	Reason For Issue	Auto Issue		

Sodium-calcium mixed partial salt of poly(methylvinylether/maleic acid) and carboxymethylcellulose

208397

Final Clinical Protocol, 20 Oct 2017

- Assess subject eligibility.
- Randomise subject to treatment group.

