7.1.5 Food Migration Adequacy Determination

Subjects must complete the food migration adequacy assessment whilst using no denture adhesives/fixatives. Dentures should have been cleaned and dried by the study staff and replaced in the subject's mouth. Subjects will be provided with 30-32 grams (accurately weighed) of non-salted peanuts, divided into smaller portions of approximately eight peanut halves by the study staff. Each portion should be chewed by the subject for approximately 20 seconds, after which the subject will be instructed to swallow at anytime they are comfortable. Subjects will be allowed small sips of water during the peanut consumption to aid chewing as appropriate. After completion of the peanut consumption, the subject will rinse their mouth with water for five seconds before removing their denture. Subjects will be asked to remove their dentures (the examiner may assist in this if required) and place them into a labelled tray (with subject screening number) teeth side down, and may remove any residual peanut particles from their mouth with water and a gauze pad (not for collection). The amount of food particles on each denture will be visually assessed by the examiner according to the scale below and recorded in the CRF to determine if there is evidence of peanut particle migration under the dentures. The following 0 – 3 assessment scale will be used. Subjects who present no evidence of peanut particles under either the upper or lower denture (i.e. if either denture scores as 0) will not be eligible.

The location and extent of peanut particle migration will be rated as follows:

GlaxoSmithKline Consumer Healthcare Confidential

Template Version Effective: 22-Jun-2017

Page 32 of 62

 GlaxoSmithKline	Document Name	208397 Clinical Protocol 2.docx		
	Type	Version	Document Identifier	Effective Date
	eldo_controlled	2.0; Most Recent; Effective; CURRENT	090032d580db1b91	24-Oct-2017 08:49:05
	Reason For Issue	Auto Issue		

Sodium-calcium mixed partial salt of poly(methylvinylether/maleic acid) and carboxymethylcellulose

208397

Final Clinical Protocol, 20 Oct 2017

0= None – No peanut migration under the denture.

1= Minimal – Slight migration of peanuts under the denture.

2= Moderate – Migration of peanuts over the internal walls of the denture.

3= Extensive – Peanuts migration on the crest of the denture.

Dentures should be cleaned thoroughly by the study staff prior to returning to the subject.

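### Visit 1 lists the 30-32 g peanut test before the criteria review, and no text requires the nut-allergy and choking exclusions to be applied first

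*Protocol*

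**What the plan says.** Protocol section 6.1.1 (Screening - Visit 1) opens its list with "The following procedures/assessments will take place in the order listed below (where possible), and recorded in the CRF". The list runs from consent through the histories, the oral soft tissue examination, denture cleaning and the two denture assessments to the Food Migration Adequacy Assessment. The criteria review and the eligibility decision follow that test.

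Section 7.1.5 describes the test: "Subjects will be provided with 30-32 grams (accurately weighed) of non-salted peanuts". The subject chews and swallows them in small portions. The weight is the same as on a treatment day (section 7.2.1).

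Section 4.2 excludes subjects under criterion 8, "History of swallowing difficulties or choking", and criterion 11, "Known allergy to peanuts or any other nut".

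Section 3 says who goes on to the test: "Only those subjects with dentures (both upper and lower) that satisfy both of these criteria will undergo the food migration adequacy assessment". The two criteria meant there are denture fit and denture make. SAP section 1.1 repeats the statement.

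**The concern.** An exclusion that protects against an exposure has to be applied before that exposure. Section 1.2.1 ties the nut-allergy exclusion to the peanuts: they may be contaminated with other nuts, so any nut allergy excludes. Section 5.8 foresees anaphylaxis to the study peanuts. The protocol gives no reason for the choking exclusion, but its relevance to swallowing 30-32 g of nuts is a fair inference.

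A site that follows the Visit 1 list as written formally applies both exclusions only after the subject has eaten the peanuts. What is at stake is the safety of screenees. The trial's estimates are not involved.

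**Working it through.** No arithmetic applies. The check has three parts: the position of each step in the Visit 1 list, a search for any other text that would put the allergy or choking check first, and a test of whether the late review is needed.

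**1. Positions in the section 6.1.1 list (13 items)**

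| Item | Step | Bearing on exclusion criteria 8 and 11 |
|---|---|---|
| 1 | Consent | Hazards are explained (section 7.1.1); no eligibility decision |
| 3 | Medical history | May reveal either condition; the item names only drug, alcohol and tobacco use |
| 4 | Dental history | Section 7.1.2 does not mention allergy or swallowing |
| 8, 9 | Well-made and well-fit assessments | Dentures only |
| 10 | Food Migration Adequacy Assessment | First peanut exposure |
| 11 | Review of inclusion and exclusion criteria | Criteria formally applied |
| 12 | Eligibility decision | Final decision |

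**2. Other text that could place the check earlier**

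- Section 3 and SAP section 1.1 make good fit and make a condition for the test. They do not mention allergy or choking.
- Section 7.1.5 contains no allergy or choking check. The only ineligibility it states is a migration score of 0 on either denture.
- Section 4.1 requires eligibility to be assessed before enrolment, and section 4.3 requires all criteria to be met for randomisation. Neither refers to the screening peanuts.
- Section 5.7 has allergies recorded in the CRF. It does not say that they must be acted on before the test.
- Section 11.3.4 allows a generic pre-screening questionnaire but does not require one.

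None of these requires criteria 8 and 11 to be applied before item 10.

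**3. Whether the late review is needed**

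Inclusion criterion 8d (a migration rating above 0 for each denture) needs the peanut result, so that check has to follow item 10. Inclusion criteria 8b and 8c need only items 8 and 9, which are already done. Exclusion criteria 8 and 11 need only history. Of the criteria discussed here, 8d alone has to wait.

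**A related point on recording.** Section 8.2.1 collects adverse events only from first treatment use at Visit 2, and sends earlier occurrences to medical history. A non-serious reaction to the screening peanuts would therefore not be recorded as an adverse event. Serious events are recorded from consent (section 8.2.2).

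**The case against.** The case for the present text is substantial, and several parts of it stand.

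- The order is qualified in its own opening sentence, so a site may check earlier. This stands, but permission to check earlier is not a requirement to do so.
- Items 11 and 12 can be read as closing out eligibility once the denture and peanut results are in. At Visits 2-4 those results already exist, which explains why the review comes first there. This stands for criterion 8d. It gives no reason for criteria 8 and 11 to wait.
- The relevant information should surface before the peanuts. Consent comes first and must cover hazards, medical history follows, and criterion 11 concerns a known allergy. This stands and narrows the risk considerably. What is missing is an instruction to act on that information before the test. The consent form is not available, so its wording on allergy cannot be judged.

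A reader might also infer stronger points that the documents do not support.

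- *That Table 1-1 contradicts section 6.1.1.* Its "Review Inclusion/Exclusion criteria" row stands directly below consent and above food migration adequacy. However, the table is described as an overview and sets no order. Its rows depart from the listed sequence elsewhere: denture photographs stand above the questionnaire, whereas section 6.1.2 lists the questionnaire first.
- *That older allergies would go unasked.* Section 5.7 reads "Details of any relevant dental, medical or surgical history (within the last year), including allergies or drug sensitivity, will be recorded in the CRF". The time limit governs what is recorded, the sentence expressly includes allergies, and the history item in section 6.1.1 has no time limit. A standing nut allergy is also a current condition, and SAP section 4.2.2 lists current conditions.
- *That denture fit and make alone admit a subject to the test.* Section 3 states a necessary condition. It does not call it sufficient.
- *That the temporomandibular joint exclusion (criterion 10) adds to the safety argument.* Section 1.2.1 ties it principally to the ability to chew.

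**Conclusion.** The point holds as a gap in sequence. The Visit 1 list places the peanut test one step before the criteria review, and nothing in the protocol or SAP requires exclusion criteria 8 and 11 to be applied before that first exposure.

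Those at risk are screenees who have an excluding condition that is missed, or not acted on, at consent and history. The documents give no prevalence of nut allergy or choking history among screenees, so no count can be given. A reader might take everyone who reaches the test, or the approximately 48 (maximum 50) enrolled, as the number affected. That does not follow: under section 4.3, correctly randomised subjects have met every criterion, and a screenee without an excluding condition loses nothing by the order.

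The probability of harm is unknown and may be low. The possible harm is serious, since the protocol itself names anaphylaxis. The conclusion assumes that sites follow the list as written and that no separate site instruction or consent wording already imposes the check. No endpoint, estimate or sample size is touched.

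**What to change.** Reconcile the Visit 1 order with the exclusion criteria.

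1. In section 6.1.1, list the review of every criterion that does not depend on the peanut result, in particular exclusion criteria 8 and 11, before the Food Migration Adequacy Assessment. Placing it after the well-fit assessment lets inclusion criteria 8b and 8c be settled at the same step.
2. Leave only inclusion criterion 8d and the final eligibility sign-off after the test.
3. In sections 3 and 7.1.5, state that subjects go on to the peanut test only once that earlier review is passed.

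The cost is one moved list item, split so that 8d stays behind, and a sentence in each of two sections. No procedure is added, and subjects with an excluding condition are stopped earlier in the visit.

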6.2 Subject Withdrawal

At the end of the study subjects will be evaluated to determine if they completed all study procedures or if they were discontinued from the study early. If the subject discontinued at any point during the study, the primary reason for withdrawal should be recorded on the Study Conclusion page of the CRF by selecting one of the options below.

1. Subject did not meet study criteria
2. Adverse event
3. Subject lost to follow up
4. Protocol Violation
5. Withdrawal of informed consent
6. Other

Subjects may withdraw from the study at any time at their own request, or they may be withdrawn at any time at the discretion of the investigator or sponsor for safety or, behavioural reasons, or the inability of the subject to comply with the protocol-required schedule of study visits or procedures at a given study site.

The following circumstances require discontinuation of study treatment and/or premature subject withdrawal:

- Protocol violation that may impact the outcome of the subject's safety
- Withdrawal of informed consent
- Subject lost to follow-up
- Pregnancy
- Death

If a subject is discontinued or prematurely withdraws from the study, reasons for discontinuation or withdrawal and associated date must be documented in the relevant section(s) of the CRF.

If a subject does not return for a scheduled visit, every effort should be made to contact the subject. The Investigator or site staff should attempt to contact the subject twice. After two attempts, clinical site staff must send a registered letter. If no response is received from the subject, the subject will be considered lost to follow up. All attempts to contact the subject and information received during contact attempts must be documented in the CRF. In any circumstance, every effort should be made to document subject outcome, if possible. The

 GlaxoSmithKline	Document Name	208397 Clinical Protocol 2.docx		
	Type	Version	Document Identifier	Effective Date
	eldo_controlled	2.0; Most Recent; Effective; CURRENT	090032d580db1b91	24-Oct-2017 08:49:05
	Reason For Issue	Auto Issue		

Sodium-calcium mixed partial salt of poly(methylvinylether/maleic acid) and carboxymethylcellulose

208397

Final Clinical Protocol, 20 Oct 2017

investigator should inquire about the reason for withdrawal, request that the subject return for a final visit, if applicable, and follow-up with the subject regarding any unresolved AEs.

It may be appropriate for the subject to return to the clinical site for final safety assessments. Subjects should be questioned regarding their reason for withdrawal. An OST examination may be conducted at the investigator's discretion.

Lack of completion of all or any of the early termination procedures will not be viewed as protocol deviations so long as the subject's safety was preserved.

If the subject withdraws from the study and also withdraws consent for disclosure of future information, no further evaluations should be performed and no additional data should be collected. The sponsor may retain and continue to use any data collected before such withdrawal of consent.

